--	--

11) To describe, in adults 18-55 years previously vaccinated with any COVID-19 vaccine, the immune response a booster dose of CoV2 preS dTM-AS03 (B.1.351) or CoV2 preS dTM-AS03 (D614 + B.1.351).
 
12) To compare the neutralizing antibody profile to the B.1.351 variant at D15 in each study Intervention Group and D36 in the Comparator Group, overall, by priming platform, and by priming vaccine.
 
13) To compare the neutralizing antibody profile against the D614G strain at D15 following a booster dose of CoV2 preS dTM-AS03 (D614 + B.1.351) and at D36 in the Comparator Group.
 
14) To describe, among adults previously primed with CoV2 preS dTM-AS03 (D614) vaccine, the immune response induced by a booster dose of CoV2 preS dTM-AS03 (D614) or CoV2 preS dTM-AS03 (B.1.351) or CoV2 preS dTM-AS03 (D614 + B.1.351) vaccine, overall, by priming dose, and by age.
 
15) To assess the neutralizing antibody profile to the D614G strain at D29, D91, D181, and D366 in each study Intervention Group, overall, by age group, by priming platform, and by priming vaccine.
 
16) To assess the neutralizing antibody to the B.1.351 variant at D29, D91, D181, and D366 in each study Intervention Group, overall, by age group, by priming platform, and by priming vaccine.
 
17) To describe, in adults over 55 years of age, the neutralizing antibody profile to the B.1.351 variant and to the D614G strain at D01 and D15 by Intervention Group, overall, by priming platform, and by priming vaccine.
 
18) To describe in adults previously vaccinated with the Pfizer/BioNTech COVID-19 mRNA vaccine the immune response (as assessed by pseudovirus neutralization assay geometric mean titers and geometric mean titer ratios) to a booster dose of CoV2 preS dTM-AS03 (B.1.351) exploratory formulations, overall and by age stratum.
 
19) To assess the binding antibody profile at D01, D15, D29, D91, D181, and D366 after booster immunization in adults previously vaccinated with COVID-19 vaccines, overall and by age group, by priming platform, and by priming vaccine.
	
 Individual serum neutralization titer fold-rise postvaccination relative to D01 at D15 profile to the B.1.351 variant in each Intervention Group ≥ 2-fold-rise and ≥ 4-fold-rise in serum neutralization titer [post/pre] (fold-rise ≥ 2 and ≥ 4) at D15 relative to D01 profile to the B.1.351 variant in each study Intervention Group Seroresponse rate, defined as a 4-fold-or greater rise in serum neutralization titer [pre/post] at D15 relative to D01, profile to the B.1.351 variant in each study Intervention Group 
Endpoints for secondary objectives #15 and #16: neutralizing responses to be evaluated against the D614G strain and to the B.1.351 variant
 
 Individual serum neutralizing titers in each Intervention Group at each pre-defined timepoint Individual serum neutralization titer fold-rise postvaccination at each pre-defined timepoint relative to D01 in each Intervention Group ≥ 2-fold-rise and ≥ 4-fold-rise in serum neutralization titer [post/pre] (fold-rise ≥ 2 and ≥ 4) at each predefined timepoint relative to D01 in each study Intervention Group 
Endpoints for secondary objective #17:
 
 Individual serum neutralizing titer at D01 and D15 against the D614G strain in each Intervention Group Individual serum neutralization titer fold-rise postvaccination relative to D01 at D15 against the D614G strain in each Intervention Group ≥ 2-fold-rise and ≥ 4-fold-rise in serum neutralization titer [post/pre] (fold-rise ≥ 2 and ≥ 4) at D15 relative to D01 against the D614G strain in each study Intervention Group Seroresponse rate, defined as a 4-fold-or greater rise in serum neutralization titer [pre/post] at D15 relative to D01, against the D614G strain in each study Intervention Group Individual serum neutralizing titer at D01 and D15 profile to the B.1.351 variant in each Intervention Group Individual serum neutralization titer fold-rise postvaccination relative to D01 at D15 profile to the B.1.351 variant in each Intervention Group ≥ 2-fold-rise and ≥ 4-fold-rise in serum neutralization titer [post/pre] (fold-rise ≥ 2 and ≥ 4) at D15 relative to D01 profile to the B.1.351 variant in each study Intervention Group Seroresponse rate, defined as a 4-fold-or greater rise in serum neutralization titer [pre/post] at D15
---	--

	
relative to D01, profile to the B.1.351 variant in each study Intervention Group
 
Endpoints for secondary objective #18:
 
• Individual serum neutralizing titer at D01 and D15 against the D614G strain in each Intervention Group• Individual serum neutralization titer fold-rise postvaccination relative to D01 at D15 against the D614G strain in each Intervention Group• ≥ 2-fold-rise and ≥ 4-fold-rise in serum neutralization titer [post/pre] (fold-rise ≥ 2 and ≥ 4) at D15 relative to D01 against the D614G strain in each study Intervention Group• Seroresponse rate, defined as a 4-fold-or greater rise in serum neutralization titer [pre/post] at D15 relative to D01, against the D614G strain in each study Intervention Group• Individual serum neutralizing titer at D01 and D15 profile to the B.1.351 variant in each Intervention Group• Individual serum neutralization titer fold-rise postvaccination relative to D01 at D15 profile to the B.1.351 variant in each Intervention Group• ≥ 2-fold-rise and ≥ 4-fold-rise in serum neutralization titer [post/pre] (fold-rise ≥ 2 and ≥ 4) at D15 relative to D01 profile to the B.1.351 variant in each study Intervention Group• Seroresponse rate, defined as a 4-fold-or greater rise in serum neutralization titer [pre/post] at D15 relative to D01, profile to the B.1.351 variant in each study Intervention Group 
Endpoints for secondary objective #19:
 
• Individual antibody concentration at each predefined time point• Individual antibody fold-rise post-vaccination relative to D01 at each pre-defined post-vaccination time point• 2-fold-rise and 4-fold rise (fold-rise in antibody concentration [post/pre] ≥ 2 and ≥ 4) at each predefined post-vaccination time point• Responders, defined as participants who had baseline values below LLOQ with quantifiable antibody concentration above assay LLOQ at predefined post-vaccination timepoints and participants with baseline values above LLOQ with a 4-fold increase in binding antibody concentration at each pre-defined post-vaccination timepoint
--	--

Secondary Safety
 
To describe the occurrences of laboratory-confirmed symptomatic COVID-19, overall and in each study Intervention Group
	
	
 Occurrences of laboratory-confirmed symptomatic COVID-19 (based on locally-confirmed or protocol-defined NAAT) Occurrences of symptomatic COVID-19 episodes associated with hospitalization. Occurrences of severe symptomatic COVID-19 Death associated with symptomatic COVID-19

Exploratory Immunogenicity
	

Supplemental Cohorts 1 and 2:
 
 To describe the neutralizing antibody response to emergent SARS-CoV-2 variant strains To further describe humoral immune responses based on relevant emerging assays, if applicable 
Supplemental Cohort 2:
 
 To assess the cellular immune response at D01, D15, D29, D91, and D366 in a subset of participants. To assess the mucosal antibody response at D01, D15, and D91 in a subset of participants. To describe the neutralizing antibody response to emergent SARS-CoV-2 variant strains To further describe humoral immune responses based on relevant emerging assays, if applicable 
Supplemental Cohorts 1 and 2:
 
 To describe the neutralizing antibody response, by presence or absence of baseline high-risk medical conditions 	
Endpoints for exploratory immunogenicity objective #1 and #5:
 
Neutralizing antibody responses to emergent variant strains will be measured:
 
 Individual serum neutralizing titer at each pre-defined time point Individual serum neutralization titer fold-rise post-vaccination relative to D01 at each pre-defined time point \geq 2-fold-rise and \geq 4-fold-rise in serum neutralization titer [post/pre] at each predefined post-vaccination timepoint Responders, defined as participants who had baseline values below LLOQ with quantifiable neutralization titer above assay LLOQ at each pre-defined post-vaccination timepoint and participants with baseline values above LLOQ with a 4-fold increase in neutralizing antibody titers at each pre-defined post-vaccination timepoint 
Endpoint for exploratory immunogenicity objective #2 and #6:
 
Biomarker measurement at baseline and/or post-vaccination visits
 
Endpoint for exploratory immunogenicity objective #3:
 
 Other CMI assessments may be performed by Intracellular Cytokine Staining or/and enzyme-linked immunospot (ELISpot) assays. 
Endpoints for mucosal antibody responses (objective #4) will be specified in a supplemental analysis plan
 
Endpoints for exploratory immunogenicity objective #7:
 
Neutralizing antibody responses to D614G and B.1.351 strains will be measured:
 
 Individual serum neutralizing titer at each predefined time point Individual serum neutralization titer fold-rise post-vaccination relative to D01 at each pre-defined time point \geq 2-fold-rise and \geq 4-fold-rise in serum neutralization titer [post/pre] at each predefined post-vaccination timepoint

	
• Responders, defined as participants who had baseline values below LLOQ with quantifiable neutralization titer above assay LLOQ at each pre-defined post-vaccination timepoint and participants with baseline values above LLOQ with a 4-fold increase in neutralizing antibody titers at each pre-defined post-vaccination timepoint
--	--

3 Statistical Considerations

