Study intervention groups and assignment method	
Participants will be screened for eligibility criteria at the time of inclusion.
 
 Supplemental Cohort 1: previously vaccinated participants will be stratified based on the priming vaccine received 4 to \leq 10 months prior and by age group (18-55 years of age and 56 years of age and older) and will receive a single booster dose of CoV2 preS dTM-AS03 (D614). Supplemental Cohort 2, Main Arms: Participants previously vaccinated with an authorized/approved mRNA or adenovirus-vectored COVID-19 vaccine will be stratified based on the vaccine received 4 to \leq 10 months prior and by age group (18-55 years of age and 56 years of age and older) and randomly assigned to 1 of the following booster formulations in a 1:1 ratio: 
 CoV2 preS dTM-AS03 (B.1.351) CoV2 preS dTM-AS03 (D614 + B.1.351) Participants previously vaccinated with CoV2 preS dTM-AS03 (D614) as a primary series in the Original Phase II Cohort will be stratified by age group (18-55 years of age and 56 years of age and older) and randomly assigned to 1 of the following booster formulations in a 9:1 ratio for younger adults (D614:B.1.351) and a 1:1 ratio for older adults: 
 CoV2 preS dTM-AS03 (D614) CoV2 preS dTM-AS03 (B.1.351) Supplemental Cohort 2 Exploratory B.1.351 Arms: participants previously vaccinated with the Pfizer/BioNTech mRNA vaccine

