	
• Primed with J&J/Janssen:
○ 18-55 years of age: 75 participants○ 56 years of age and older: 25 participants
	
Supplemental Cohort 2, Main Arms: adults vaccinated 4 to \leq 10 months prior will be stratified by primary vaccine and by age and randomized to receive 1 of the following as a single booster dose:
 
• Primed with Pfizer/BioNTech:
○ CoV2 preS dTM (D614 + B.1.351):
■ 18-55 years of age: 515 participants■ 56 years of age and older: 50 participants○ CoV2 preS dTM (B.1.351):
■ 18-55 years of age: 515 participants■ 56 years of age and older: 50 participants• Primed with CoV2 preS dTM-AS03 (actual numbers will depend on eligibility and consent for Cohort 2 participation of participants enrolled in the Original Phase II Cohort; numbers below are estimates and subject to change):
○ CoV2 preS dTM-AS03 (B.1.351):
■ 18-55 years of age: 30 participants■ 56 years of age and older: 75 participants○ CoV2 preS dTM-AS03 (D614):
■ 18-55 years of age: 270 participants■ 56 years of age and older: 75 participants• Primed with Moderna:
○ CoV2 preS dTM-AS03 (D614 + B.1.351):
■ 18-55 years of age: 75 participants■ 56 years of age and older: 25 participants○ CoV2 preS dTM-AS03 (B.1.351):
■ 18-55 years of age: 75 participants■ 56 years of age and older: 25 participants• Primed with Oxford University/AstraZeneca:
○ CoV2 preS dTM-AS03 (D614 + B.1.351):
■ 18-55 years of age: 75 participants■ 56 years of age and older: 25 participants○ CoV2 preS dTM-AS03 (B.1.351):
■ 18-55 years of age: 75 participants■ 56 years of age and older: 25 participants• Primed with J&J/Janssen:
○ CoV2 preS dTM-AS03 (D614 + B.1.351):
■ 18-55 years of age: 75 participants■ 56 years of age and older: 25 participants

	
○ CoV2 preS dTM-AS03 (B.1.351):
▪ 18-55 years of age: 75 participants▪ 56 years of age and older: 25 participants

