A total of 515 participants, 18-55 years of age, who are SARS-CoV-2 naïve (no evidence of previous infection or vaccination) receiving 2 doses of the CoV2 preS dTM-AS03 (D614) parental vaccine will be enrolled as the Comparator Group for both Supplemental Cohorts 1 and 2. Additionally, for enabling extrapolation, approximately 50 participants ≥ 56 years of age are planned to be enrolled in each Supplemental Cohort 1 and Cohort 2 groups primed with the Pfizer/BioNTech vaccine (in the non-exploratory arms).

Approximately 300 participants, 18-55 years of age, primed with the CoV2 PreS dTM-AS03 vaccine and 150 participants, ≥ 56 years of age, primed with the CoV2 PreS dTM-AS03 vaccine are assumed to transition from the Original Phase II Cohort into the 2 Supplemental Cohort 2 vaccine groups, CoV2 preS dTM-AS03 (B.1.351) and CoV2 preS dTM-AS03 (D614); however, the actual number of Original Phase II Cohort participants meeting eligibility criteria for transition cannot be accurately determined, and as such the actual number of CoV2 PreS dTM-AS03 booster participants in Supplemental Cohort 2 may be smaller or larger than assumed. For detailed power estimations for Supplemental Cohorts 1 and 2 refer to [Table 3.1](#).

Table 3.1: Power estimations for Supplemental Cohorts 1 and 2 (18-55 years old)

Cohort/ Objective(s)	Arm	Parameters for Non- inferiority	Parameters for Superiority	Study Power
Cohort 1 CoV2 preS dTM-AS03 (D614) Booster Group				
Primary Objectives (Type I error: 0.00833)	Pfizer primed CoV2 preS dTM-AS03 (D614) Booster Group (N=215)	
 Assumed true ratio of group GMT: 1.5 Margin: 1/1.5 Std Dev (booster): 1.0 Std Dev (comparator): 0.65 	
 Assumed true ratio: 5 Margin: 2 Std Dev (booster): 1.0 	
 Non-inferiority: 98.7% Superiority: > 99.9% Overall: 98.7%
Conditional Secondary Objectives (Type I error: 0.00833)	CoV2 preS dTM-AS03 (D614)primed CoV2 preS dTM- AS03 (D614) Booster Group (N=270)			
 Non-inferiority: 99.7% Superiority: > 99.9% Overall: 99.6%
Conditional Secondary Objectives (Type I error: 0.00833)	mRNA primed CoV2 preS dTM- AS03 (D614) Booster Group (N=290)			
 Non-inferiority: 99.8% Superiority: > 99.9% Overall: 99.8%

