The Geometric mean of titer ratio is defined as:

$$GMTR = \left(\prod_{i=1}^n ratio_i \right)^{\frac{1}{n}} = 10^{\frac{\sum_{i=1}^n \log_{10}(ratio_i)}{n}} = 10^{\frac{\sum_{i=1}^n \log_{10}\left(\frac{post_i}{pre_i}\right)}{n}}$$

The normal approximation will be used to calculate the 2-sided 98.3% CIs for the individual group GMTRs as follows:

$$10^{(\bar{x} \pm t_{n-1, \alpha/2} \sqrt{v(\bar{x})})}$$

where $10^{(\bar{x})}$ is the GMTR, $\bar{x} = \frac{1}{N} \sum \log_{10}(x)$, $\log_{10}(x)$ is the log base 10 of the titer ratio (post/pre), N is the number of subjects with non-missing value for pre and post-vaccination,

$\sqrt{V(\bar{x})}$ is the estimated standard deviation of \bar{x} , and $t_{n-1, \alpha/2}$ is the 100(1- $\alpha/2$) percentile of the central t -distribution with $n-1$ degrees of freedom.

The margin used for superiority hypothesis testing are 2 for individual group GMTRs. The superiority in terms of GMTRs will be demonstrated if the lower limit of the 2-sided 98.3% CI (Supplemental Cohorts 1 and 2) for the mean of \log_{10} (GMTRs) $> \log_{10}(2)$.

GMTs in each injection group and GMT ratios between injection groups will be descriptively summarized along with their 95% CIs using the normal approximation of log-transformed titers. GMTs will be presented in original scale that are re-converted from log-transformed titers. The 95% CI of GMT ratios between booster arms and comparator group will base on the Welch's t-interval for Supplemental Cohort 1 and 2 will base on the Student t-distribution.

Analyses will be performed for both FAS and PPAS, but the conclusion will be made mainly from results based on PPAS and supported by results based on FAS.

Subgroup analyses, where applicable, will be performed by age-group (18-55 years and ≥ 56 years) for intervention groups, by priming vaccine (Supplemental Cohorts 1 and 2), and by priming platform (Supplemental Cohorts 1 and 2), in addition to the Overall group.

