Lower bound: $1 - Beta(1 - \alpha / 2, n - r + 1, r)$ and

Upper bound: $Beta(1 - \alpha / 2, r + 1, n - r)$

where r is the observed number of events/responders in n observations.

GMTs or GMCs in each injection group and GMT or GMC ratios between injection groups will be descriptively summarized along with their 95% CIs using the normal approximation of log-transformed titers. GMTs or GMCs will be presented in original scale that are re-converted from log-transformed titers. The 95% CI of GMT or GMC ratios between booster arms and comparator group will base on the Welch's t-interval for Supplemental Cohort 1 and 2.

The 95% CI of GMT ratios after booster dose at D15 between booster arms based on the Student t-distribution and 95% CI of difference on seroresponse rate at D15 relative to D01 between booster arms based on the Newcombe-Wilson score method without continuity correction will be provided for homogeneity/comparability evaluation on booster effect across different primary series vaccines, by age group and overall.

GMTRs or GMCRs is defined as ratio of individual geometric mean titer or concentration for each injection group (post-vaccination/pre-vaccination for each injection). GMTR or GMCR will be summarized with 95% CI (Normal approximation). Additional parameters may be displayed as appropriate.

Confidence interval for the individual group GMT or GMC and GMTR or GMCR

The normal approximation will be used to calculate the 2-sided 95% CIs for the individual group GMT or GMC and GMTRs or GMCRs as follows:

$$10^{(\bar{x} \pm t_{n-1, \alpha/2} \sqrt{v(\bar{x})})}$$

where $10^{(\bar{x})}$ is the GMT or GMC, $\bar{x} = \frac{1}{N} \sum \log_{10}(x)$, $\log_{10}(x)$ is the log base 10 of the observed titer or concentration, N is the total observation in each injection group, $\sqrt{V(\bar{x})}$ is the estimated standard deviation of \bar{x} , and $t_{n-1, \alpha/2}$ is the 100(1- $\alpha/2$) percentile of the central t -distribution with $n-1$ degrees of freedom.

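### Pooled overall ratios that involve the protein-primed B.1.351 arm are confounded by age, because allocation is 9:1 in younger and 1:1 in older adults and section 3.4.4 makes no age adjustment

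*SAP*

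**What the plan says.** Table 1.1 stratifies participants primed with the sponsor's own protein vaccine by age and randomises them to the D614 or B.1.351 booster "in a 9:1 ratio for younger adults (D614:B.1.351) and a 1:1 ratio for older adults". Section 3.2 assumes "Approximately 300 participants, 18-55 years of age, primed with the CoV2 PreS dTM-AS03 vaccine and 150 participants" aged 56 or over will transfer. Table 1.1 then gives the B.1.351 arm "18-55 years of age: 30 participants" and the D614 arm "18-55 years of age: 270 participants", with 75 older adults in each. Table 1.1 marks these counts as estimates.

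Three places create pooled summaries:

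- Table 2.1, Cohort 2 secondary objective 14, describes the protein-primed response to D614, B.1.351 or "CoV2 preS dTM-AS03 (D614 + B.1.351) vaccine, overall, by priming dose, and by age".
- Section 3.4.2 reports age group, priming vaccine and "by priming platform (Supplemental Cohorts 1 and 2), in addition to the Overall group".
- Section 3.4.4 summarises GMT ratios between injection groups. It also gives Student-t intervals for D15 GMT ratios between booster arms, and Newcombe-Wilson intervals for seroresponse differences, for "homogeneity/comparability evaluation on booster effect across different primary series vaccines, by age group and overall".

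All these intervals are plain two-sample intervals. Sections 3.4.1 to 3.4.4 contain no age covariate, stratum weighting or standardisation.

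**The concern.** Randomisation makes the D614 and B.1.351 groups comparable within each age stratum. When the allocation ratio differs between strata, the pooled groups differ in age by construction, and a crude pooled ratio carries part of any age effect on titer. Protein-primed adults are the only participants randomised between these two boosters, so this is the one place where the SAP could support a randomised D614-versus-B.1.351 description.

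The comparison across priming vaccines that section 3.4.4 does name is exposed in the same way. The B.1.351 recipients are mostly older if protein-primed and mostly younger if Pfizer-primed. A reader of the overall row could take an age difference for a strain or priming difference, or miss a real one.

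**Working it through.** **Inputs.** Counts come from Tables 1.1 and 1.2. The log10 SD of 1.0 for booster titers comes from section 3.2. The young/old GMT ratio r is assumed, because the SAP states none.

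**1. Reproduce the plan's counts.** Younger: 300 × 0.9 = 270 and 300 × 0.1 = 30. Older: 150 × 0.5 = 75 and 75. The D614 total is 270 + 75 = 345, as in Table 1.2. The protein-primed B.1.351 total is 30 + 75 = 105.

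**2. Age mix (share aged 56 or over).**

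- Protein-primed, D614: 75/345 = 21.7%
- Protein-primed, B.1.351: 75/105 = 71.4%
- Pfizer-primed, B.1.351 main arm: 50/565 = 8.8%

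The gap is 0.714 − 0.217 = 0.497 for D614 versus B.1.351, and 0.714 − 0.088 = 0.626 for protein versus Pfizer priming among B.1.351 recipients.

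**3. Sensitivity to the transfer numbers.** For seven assumed pairs of younger and older transfers (300/150, 200/150, 300/100, 150/150, 300/50, 100/150, 400/100) the first gap is 37 to 50 points. A more extreme 400/50 gives 360/385 − 40/65 = 32 points. The imbalance comes from the ratios, not from the exact counts.

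**4. Distortion of a crude GMT ratio.** With no true strain or priming effect, log GMT in each group is the average of the two age strata, so the crude ratio equals r raised to the gap in age share:

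| Assumed r | D614 / B.1.351, protein-primed: r^0.497 | Pfizer / protein, B.1.351 recipients: r^0.626 |
|---|---|---|
| 1.0 | 1.00 | 1.00 |
| 1.25 | 1.12 | 1.15 |
| 1.5 | 1.22 | 1.29 |
| 2.0 | 1.41 | 1.54 |

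A crude seroresponse difference shifts by the same gap (0.497 or 0.626) times the age difference in the rate.

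**5. Where it is small.** Among D614 recipients, protein-primed adults are 21.7% older and Cohort 1 Pfizer-primed adults 50/265 = 18.9%. The problem is concentrated in the B.1.351 arm.

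**6. Precision of an age-stratified D614-versus-B.1.351 ratio (SD 1.0).** The factor is 10^(1.96 × SE).

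- Crude: SE = √(1/345 + 1/105) = 0.111, factor 1.65
- Stratified, weights 2/3 and 1/3: SE = √[(2/3)²(1/270 + 1/30) + (1/3)²(2/75)] = 0.139, factor 1.88
- Stratified, inverse-variance weights: information 27 + 37.5 = 64.5, SE = 1/√64.5 = 0.125, factor 1.75
- Single strata: 2.38 (18-55) and 2.09 (56 and over)

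**7. Objective 14 against the allocation.** Objective 14 includes the bivalent booster among protein-primed adults. Table 1.1 offers them D614 or B.1.351 only, and the bivalent cells of Table 1.2 for this priming group are empty.

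**The case against.** The strongest reply is that no conclusion of the trial depends on these rows, and most of it stands. Every primary and conditional secondary test is confined to 18-55 years. Objective 14 is descriptive, its endpoints are per-group summaries, and results by age are already planned. The 9:1 ratio has a use: it supplies the 270 younger adults behind the protein-primed power figures in Table 3.1. The unequal allocation is therefore not itself an error.

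A reader might also infer more than the document supports:

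- **That the SAP has a headline overall D614-versus-B.1.351 ratio in protein-primed adults.** None is named. It arises only from the general sentence on ratios between injection groups. The explicit Student-t ratios compare priming vaccines, a comparison that has its own age imbalance in the B.1.351 arm.
- **That the bias matches the 1.5-fold margin.** That would need r of about 1.5^(1/0.497) = 2.26. The margin also belongs to a different contrast, booster against naive comparator in younger adults.
- **That objectives 17 and 18 share the defect.** Objective 17 sets out "To describe, in adults over 55 years of age, the neutralizing antibody profile to the B.1.351 variant and to the D614G strain" and already breaks results down by priming. In older adults 75/200 = 37.5% of the B.1.351 main-arm group is protein-primed and none of the bivalent group, but no monovalent-versus-bivalent ratio is specified there. The four exploratory arms of objective 18 are all 75 + 25 and so balanced with each other. A contrast with the main arm is not named, and would be non-concurrent, which stratifying by age would not cure.

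What remains is that following section 3.4.4 as written yields unadjusted overall between-group estimates, and planned by-age rows do not correct the overall row beside them.

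**Conclusion.** The point holds, within limits. The 49.7-point and 62.6-point age gaps follow from the SAP's planned counts and would change with actual transfer numbers. The distortion of the overall GMT ratios depends on an age effect that the SAP does not give: nil at r = 1, and between 1.12 and 1.54 for r from 1.25 to 2 across the two contrasts. It affects descriptive overall rows that include the protein-primed B.1.351 arm. The formal tests and the by-age results are sound on this point. The mismatch between objective 14 and Tables 1.1 and 1.2 needs no assumption.

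**What to change.** In section 3.4.4:

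- Compute each overall between-booster GMT ratio and seroresponse difference stratified by age group, for example log10 titer on group plus age stratum, or age-stratum differences combined with common weights. Alternatively, omit the overall row and report by age group only.
- For booster-strain contrasts pooled over priming vaccines, stratify by priming vaccine as well, and use only the strata in which both boosters were randomised.
- Do not stratify by priming vaccine where priming vaccine is the factor being compared, since that would remove the contrast. Such comparisons remain non-randomised even after age stratification, and the text should say so.

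Reconcile objective 14 with Tables 1.1 and 1.2 on the bivalent booster in protein-primed adults.

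The cost is SAP wording and a stratified calculation on an existing randomisation factor, with no new data. Intervals widen somewhat: for protein-primed D614 versus B.1.351 at log10 SD 1.0, the 95% half-width factor goes from 1.65 to between 1.75 and 1.88.
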